9.4 Safety Analysis

Adverse events will be coded using MedDRA dictionary. Incidence of adverse events by the severity, relationship to treatment, and outcome will be provided. Narratives of all serious adverse events and events causing death will be included. Laboratory parameters, vital signs and other safety parameters will be documented with the use of descriptive statistics.

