- To evaluate the safety of FMT in MS patients
- To evaluate tolerability of FMT in MS patients

Trial Design:

The proposed randomized, open label, controlled [treatment as usual control group], crossover study will be conducted in 40 patients (n=20 per group) diagnosed with the relapsing forms of multiple sclerosis according to the McDonald 2010 Criteria¹.

Based on the diagnostic criteria patients will be further screened to confirm eligibility and if eligible then consented.

Patients will be randomized 1:1 into two groups. One group will receive FMT, done by rectal enema administered by a RN, at baseline, month 1, month 2, month 3, month 4, and month 5 (early intervention group). The other group will receive treatment as per standard of care (treatment as usual control group) in the beginning of the study. For the last 6 months they will also receive FMT at month 6, month 7, month 8, month 9, month 10, and month 11 (late intervention group).

Clinical visits for both groups will be performed at baseline, and months 1 to 12 inclusive. During these visits a physical exam with vital signs, including a standardized neurological assessment Expanded Disability Status Scale – EDSS) will be done.

Patient's stools will be collected before each FMT procedure in both groups to evaluate gut microbial composition.

Urine will be collected to evaluate gut permeability at baseline, 6 and 12 months for both groups.

Peripheral blood samples also will be collected to evaluate circulating cytokine levels (IL-1 β , IL-2, IL-4, IL-5, IL-6, IL-9, IL-10, IL-12p70, IL-13, IL- 15, IL-17A, IL-17E/IL-25, IL-17F, IL-21, IL-22, IL-23, IL-27, IL-28A, IL-31, IL-33, GM-CSF, IFN γ , MIP-3 α , TNF α and TNF β) at baseline, months 1 to 12 inclusive for both groups.

Peripheral blood samples will also be collected to evaluate blood DNA bacteria at baseline, and months 1 to 12 inclusive for both groups.

Brain MRI with gadolinium [3T MRI machine at Robarts Research Institute] will be performed at baseline, 6 and 12 months for both groups as a safety biomarker [to rule out paradoxical effects; i.e. significant increase in MS activity as defined by Cutter's rule: 5 or more newly enhancing white matter lesions in the brain compared to the previous scan].

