More recently Wang et al published a systematic review on safety of FMT. A total of 50 studies including original full-text articles, letters to the editor, abstracts of scientific conferences, case reports and case series which were published between 1913 and 2015 were reviewed. Totally 78 kinds of AEs were revealed with a total incidence rate of 28.5%. Among the 42 publications, 5 kinds were definitely and 38 kinds were probably related to FMT. The commonest FMT attributable AE was abdominal discomfort, which was reported in 19 publications. For upper gastrointestinal routes of FMT, 43.6% (89/204) patients were compromised by FMT-attributable AE, while the incidence dropped to 17.7% (76/430) for lower gastrointestinal routes. In contrast, the incidences of serious adverse events (SAEs) were 2.0% (4/196) and 6.1% (40/659) for upper and lower gastrointestinal routes, respectively. A total of 44 kinds of SAEs occurred in 9.2% patients, including death (3.5%, 38/1089), infection (2.5%, 27/1089), relapse of inflammatory bowel diseases (0.6%, 7/1089) and *Clostridium difficile* infection (0.9%, 10/1089).

The paucity of RCTs is notable. As a result, there is a dearth of high-quality evidence to guide clinicians and policymakers on how to apply this promising but largely untested therapy. The overall low quality of the available evidence evaluating FMT is important and indicates that additional research is needed. However, the information available suggests that FMT can be safely done.

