8.2 Adverse events

8.2.1 Definition of an Adverse Event

An adverse event (AE) is defined as any undesirable physical, psychological, or behavioural event experienced by a subject in conjunction with their participation in the clinical trial, regardless of whether the event is procedure- or study product-related. This includes any condition (including a pre-existing condition) that was:

- Not present prior to study treatment initiation but appeared or reappeared following initiation of study treatment.
- Present prior to study treatment, but worsened during study treatment. (This could include any condition resulting from concurrent illness, reactions to concomitant medications, or progression of disease states).

The occurrence of an AE will be based on changes in the subject's physical examination, laboratory results, and/or signs and symptoms.

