9.2 Demographics

Demographic variables such as age, race, etc. and baseline status (medical history, physical exam, etc.) will be documented by dose level and/or overall, as applicable.

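### Adverse events are tabulated without randomised group, period or time at risk, so the safety tables cannot separate FMT effects from background MS events

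*Combined protocol and SAP*

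**What the plan says.** Section 9.4 (Safety Analysis) defines the AE tables in one sentence: "Incidence of adverse events by the severity, relationship to treatment, and outcome will be provided". The statistical methods paragraph of the synopsis repeats it. Neither place mentions randomised group, control or FMT period, person-time or an interval estimate. The only between-group model in the plan is the mixed-design ANOVA in section 9.3, which is for biomarkers. Baseline data in section 9.2 "will be documented by dose level and/or overall, as applicable", although the trial has no dose levels.

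The design is in the synopsis under Trial Design: "Patients will be randomized 1:1 into two groups", with 20 patients in each. The early group has its first FMT at baseline and its sixth at month 5. Of the other group it says: "For the last 6 months they will also receive FMT at month 6, month 7, month 8, month 9, month 10, and month 11". Follow-up ends at the same point for everyone: "Clinical visits for both groups will be performed at baseline, and months 1 to 12 inclusive".

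Safety is a secondary objective in the synopsis. Section 3.2 adds EDSS and MRI as markers of unexpected worsening of MS.

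The documents differ on which AEs count:

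- The synopsis records every AE in the study, and the opening sentence of section 8.2.1 covers any event linked to participation.
- The first condition listed in section 8.2.1 is "Not present prior to study treatment initiation but appeared or reappeared following initiation of study treatment".
- Section 4 describes AE review at visits after FMT.
- Section 9.7 limits all analyses to patients with one week of study treatment.

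**The concern.** Relapsing MS produces clinical events without any intervention. An event after FMT can be put in context only against patients who have not had FMT. The design supplies that comparison by randomisation for the first six months, and the safety plan does not use it. A single table by severity, causality and outcome gives counts with no reference.

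The causality column cannot replace the comparison. The criteria in section 8.2.2 turn on timing after administration and on the known response to the test product. They cannot be applied in the late group's months 0-6, when nothing has been given. The judgement is also made in an open-label trial.

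If the analyst later splits the table by exposure, the unequal follow-up after first FMT becomes a problem. A crude percentage of patients with an event rises with the length of observation. Counted from first FMT, it would not be comparable between the two groups, nor with the six control months.

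Finally, a strict reading of sections 4, 8.2.1 and 9.7 could leave control-month events uncollected or outside the analysis set. That would bias any comparison against FMT, however the tables were laid out.

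**Working it through.** The documents give no AE rate, person-time or safety precision for this trial, so there is no planned figure to reproduce.

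**Time at risk**, from the visit schedule with 20 patients per group and full follow-up:

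- Before FMT (late group, months 0-6): 20 x 6 = 120 patient-months.
- During the FMT course (early months 0-6, late months 6-12): 120 + 120 = 240.
- After the course (early group, months 6-12): 20 x 6 = 120.
- All time after first FMT: early 20 x 12 = 240, late 20 x 6 = 120, total 360.

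**Null model (assumption):** the same constant hazard in every patient-month, equal in both groups, with no FMT effect. Let p6 be the probability of at least one AE in 6 months. Then:

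- 12-month incidence: p12 = 1 - (1 - p6)^2 = 2p6 - p6^2.
- Pooled incidence after first FMT (20 patients followed 12 months, 20 followed 6): (p12 + p6)/2 = (3p6 - p6^2)/2.
- Pooled minus control months: (3p6 - p6^2)/2 - p6 = p6(1 - p6)/2.

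The last expression is largest at p6 = 0.5, where it equals 0.5 x 0.5 / 2 = 0.125.

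The true p6 is unknown, so it is varied from 5% to 90%. The 17.7% row borrows the lower-route figure (76/430) from the safety review cited in section 2.7. It serves only as an anchor, because it is neither a background rate nor a 6-month incidence.

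| p6 (control months; late group after first FMT) | p12 (early group after first FMT) | Ratio early/late | Pooled after first FMT | Pooled minus control | Ratio pooled/control |
|---|---|---|---|---|---|
| 5% | 9.8% | 1.95 | 7.4% | 2.4 points | 1.48 |
| 17.7% | 32.3% | 1.82 | 25.0% | 7.3 points | 1.41 |
| 30% | 51.0% | 1.70 | 40.5% | 10.5 points | 1.35 |
| 50% | 75.0% | 1.50 | 62.5% | 12.5 points | 1.25 |
| 90% | 99.0% | 1.10 | 94.5% | 4.5 points | 1.05 |

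Expected event counts follow person-time: 240:120 = 2:1 for early v late after first FMT, and 360:120 = 3:1 for post-first-FMT v control.

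**With equal windows or person-time**, the same null model gives a ratio of 1.00. Months 0-6 by randomised group have 120 v 120 patient-months. Per patient-month with hazard r, 360r/360 = 120r/120.

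**The case against.** The strongest reply is that section 9.4, as written, contrasts nothing with anything. A reader might infer that the planned tables would show an excess of AEs under FMT where none exists. The documents do not support that. A table without group or period makes no FMT-versus-control comparison. The 12 v 6 months contrast is between two groups that have both had FMT. By randomised group, time at risk is equal over months 0-6 and over all 12 months. The differences in the last two columns of the table arise only in a comparison that the plan does not contain. This objection stands and sets the limits of the point.

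Four further replies stand in part:

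- It is tempting to say that causal relationship is meaningless in all months without FMT. That holds only for the late group's 120 pre-FMT patient-months. In the early group's months 6-12 a delayed effect can still be judged, and section 8.2.3 provides for delayed toxicity.
- It is tempting to write into the plan that no serious AE in 40 patients is compatible with an incidence of up to 8.8% (1 - 0.025^(1/40)), above the lower-route figure in section 2.7, "2.0% (4/196) and 6.1% (40/659) for upper and lower gastrointestinal routes, respectively". But that presumes the result, takes the maximum enrolment of 40 as evaluable, and mixes 12- and 6-month follow-up. The review figure comes from other populations and is not a rate this trial sets out to exclude.
- Section 9.2 does not prescribe an overall-only baseline table. Its wording is ill-fitting and needs only a small correction.
- The study is exploratory, section 9.1 calls its size arbitrary, and narratives of serious AEs are planned. This argues against formal safety testing. It does not argue against showing safety data by randomised group.

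**Conclusion.** The point holds in a limited form. The planned AE tables cannot distinguish FMT effects from background MS events, and the randomised months 0-6 comparison is left unused for a stated safety objective. This follows from the text and needs no assumption about event rates.

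The numerical part is conditional. If crude incidence after first FMT were compared with the control months, the null difference would be p6(1 - p6)/2. It rises to 12.5 points at a 6-month incidence of 50% and falls on either side. The size rests on a constant hazard, equal groups and full follow-up. Under a common constant hazard, the direction needs only the unequal time at risk.

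The ambiguity over AE capture and the analysis set must be settled with the tables, because a by-group comparison is valid only if control-month events are collected and counted in the same way.

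**What to change.** In section 9.2, replace dose level with randomised group.

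In section 9.4 and the matching synopsis paragraph, specify:

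- (a) As the main safety comparison: patients with any AE and any serious AE, regardless of cause, by randomised group over months 0-6, with risk difference and 95% CI. Close the window before the late group's first FMT at month 6. Severity, causality and outcome tables follow the same layout.
- (b) AE rates per patient-month before, during and after the FMT course. Label them descriptive, because the before period is late group only and the after period is early group only.
- (c) An exact 95% CI for serious-AE incidence, using the observed count and denominator in a fixed window, with no pre-written sentence about zero events.

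In sections 4 and 8.2, state that AEs are collected identically at every visit from baseline in both groups. In section 9.7, define a safety set for months 0-6 that includes all randomised patients, including late-group patients who leave before FMT.

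The cost is slightly more table work and some protocol wording. Both groups already attend monthly, so no visits or patients are added. The price is a safety statement that will probably read less favourably.

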In the event of early termination, a visit will be performed whenever possible, including a final blood sample and all end of treatment assessments that should be completed as soon as possible. All patients with at least 1 week of treatment will be

eligible for analysis.

Number of Patients:

A maximum of 40 patients will be enrolled in intervention part of this study and randomized 1:1 into one of the two groups [20 patients per group] using an internet based randomizer software [<https://www.randomizer.org/>]. We may screen up to an extra 10 patients to compensate for possible drop outs, withdraw consent or those who discontinued for any other reason.

We will also recruit up to 10 healthy volunteers to provide a blood sample [1 tube, 5 ml] to serve as a reference arm for the cytokine analysis. This reference group will be seen only once and will not participate in any other study activities.

Consequently, the total number of participants in this study will be n=50.

Inclusion criteria for patients:

1. Have a confirmed diagnosis of relapsing MS defined by the 2010 Revised McDonald Criteria for the Diagnosis of Multiple Sclerosis¹
2. Have a baseline Expanded Disability Status Scale (EDSS) ≤ 7.0
3. Age equal or older than 18 years of age
4. Be able to attend all clinic appointments without interruption
5. Be proficient in English
6. Be willing and able to give written informed consent
7. Negative blood pregnancy test at screening

Exclusion criteria for patients

1. Not meeting all of the above inclusion criteria
2. Pregnancy [current or planned for the near future] or breastfeeding
3. All qualified patients will not be currently or recently [90 days] treated with immunosuppressive therapy [i.e. chemotherapy] or high dose corticosteroids [i.e. 1g of prednisone or greater or equivalent]. Immune-Modulatory therapies are allowed as per standard of care.
4. Ongoing use of antibiotics
5. Presence of a chronic intestinal disease e.g. celiac, mal-absorption, colonic tumor
6. Concomitant inflammatory diseases
7. Standard of care exclusions for MRI scans as per LHSC standards

Healthy controls Selection:

1. Age equal or older than 18
2. Written informed consent
3. Self reportedly “healthy”, in particular not having a history of any disease or

disorder, or any treatment ever for such [ie lupus, cancer, etc], that in the opinion of the PI could be possibly related to changes in the immune system that would alter the results of a cytokine in blood analysis.

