9.5 Criteria for Study Termination

The study continues until all 40 patients have been treated.

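### Section 9.4 reports adverse-event incidences with no interval, no FMT-exposure denominator and no use of the randomised untreated period, so the safety objective has no stated precision

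*Combined protocol and SAP*

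**What the plan says.** The synopsis lists as a secondary objective "To evaluate the safety of FMT in MS patients". The analysis for it is in section 9.4, repeated in the synopsis under statistical methods. Event rates are covered by one sentence: "Incidence of adverse events by the severity, relationship to treatment, and outcome will be provided". Two further outputs are planned: "Narratives of all serious adverse events and events causing death will be included", and "Laboratory parameters, vital signs and other safety parameters will be documented with the use of descriptive statistics".

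On numbers, the synopsis states "A maximum of 40 patients will be enrolled in intervention part of this study and randomized 1:1 into one of the two groups", and section 9.5 says "The study continues until all 40 patients have been treated". Both groups eventually receive FMT: the early group from baseline to month 5, the late group from month 6 to month 11. The only untreated randomised comparison therefore ends when the late group has its month 6 FMT.

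Section 2.7 supplies an external rate for the route used here (rectal enema): "the incidences of serious adverse events (SAEs) were 2.0% (4/196) and 6.1% (40/659) for upper and lower gastrointestinal routes, respectively".

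No section gives an interval, a precision target or an excludable rate for adverse events. Section 9.1 says the group sizes were chosen arbitrarily, so the sizing does not address safety.

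**The concern.** Three things are missing from 9.4.

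- **Uncertainty.** With at most 40 exposed patients, a serious-event percentage is compatible with a wide range of true rates, and the planned output does not show that range.
- **Denominator.** Everyone is eventually treated, but at different times. An incidence over all patients and all months mixes untreated months in the late group with treated months in both groups. Events are recorded whatever their cause, so MS-related events are mixed in as well.
- **The control period.** Randomisation provides six months of untreated comparison. This is the only design-based way to separate background events from those that follow FMT, and 9.4 does not use it.

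At stake is what the trial may conclude on one of its own objectives: an observed percentage standing alone, or a statement of which rates the data exclude.

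**Working it through.** **Inputs.** Patients receiving FMT: at most 40, 20 per group (synopsis; 9.5). Yardstick: 40/659 serious events for lower routes (2.7). Section 5.4 sets a 90% adherence target; if it is just met, 0.9 × 40 = 36 patients.

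**Reproducing the cited rates.** 40/659 = 6.07%, which rounds to 6.1%. 4/196 = 2.04%. The lower-route rate of FMT-attributable events is 76/430 = 17.67%. All agree with section 2.7. The plan states no safety precision to reproduce.

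**Upper limits with zero events.** Two-sided 95% (Clopper-Pearson): 1 − 0.025^(1/n). One-sided 95%: 1 − 0.05^(1/n). Probability of no event at the yardstick rate: (1 − 40/659)^n.

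| n | Two-sided limit | One-sided limit | P(no event) at 40/659 |
|---|---|---|---|
| 40 | 8.8% | 7.2% | 8.2% |
| 36 | 9.7% | 8.0% | 10.5% |
| 20 | 16.8% | 13.9% | 28.6% |

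Every limit lies above 6.1%. The yardstick itself has an exact 95% interval of 4.4% to 8.2%, and 8.8% lies above all of it.

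**Patients needed to exclude 6.1% with zero events.** ln(0.05)/ln(1 − 0.061) = 47.6, so 48 (one-sided). ln(0.025)/ln(1 − 0.061) = 58.6, so 59 (two-sided). Both exceed 40.

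**What 0 of 40 does exclude.** At a true 9%, 0.91^40 = 2.3%. At the 9.2% overall serious-event rate in 2.7, 0.908^40 = 2.1%. Both are below 2.5%, so both rates are excluded, the first narrowly.

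**Other results.** The exact 95% interval is 0.06% to 13.2% for 1 of 40, and 0.6% to 16.9% for 2 of 40. For FMT-related events near the cited 17.7% (0.177 × 40 = 7.1), 7 of 40 gives 7.3% to 32.8%.

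**Expected number at the yardstick.** 40 × 0.0607 = 2.4 patients. P(0) = 8.2% and P(1) = 40 × 0.0607 × 0.9393^39 = 21.1%, so P(0 or 1) = 29%. P(at least one) = 92%.

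**Can the control period be analysed as written?** The synopsis has all adverse events during the study recorded, and the opening sentence of 8.2.1 is equally broad. The bullets in 8.2.1, however, define events relative to the start of study treatment, and section 4 places adverse-event review at visits after FMT. Read literally, these miss events in late-group patients before month 6. Section 9.7 admits to all analyses patients with one week of treatment, without saying what that means for a monthly enema. Read literally, it drops a late-group patient who leaves before month 6, and could drop a patient who stops within days of a first FMT.

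**The case against.** The strongest reply is that this is an exploratory immunological study, for which descriptive safety reporting is common, and that any reader can compute an exact interval from a count and a denominator. The plan also gives more than event percentages: breakdowns by severity, relationship and outcome, a narrative for each serious event, EDSS at every visit, and MRI at three time points with a defined threshold for paradoxical activity. With so few events, narratives carry much of the information. All of this stands. None of it puts a limit on an event rate, and a reader can compute an interval only if the exposure denominator is reported, which 9.4 does not promise.

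Several stronger readings are tempting, and the documents do not support them.

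- *A clean result would be declared safe.* The plan has no safety hypothesis or rule for calling FMT safe. The very favourable wording in sections 5.5 and 11.5 concerns earlier studies, and section 2.7 reports deaths and serious events.
- *Zero or one serious event is the likely outcome.* At 6.1% in 40 patients its probability is 29%. It becomes likely only if the true rate is well below the yardstick.
- *Forty patients say nothing about a 6.1% rate.* At that rate at least one event would be seen with 92% probability. 0 of 40 falls short of excluding 6.1% by a modest margin, and it does exclude 9%.
- *6.1% is the expected rate here.* It comes from other patient groups and is not presented as FMT-attributable. The documents give neither its follow-up nor its number of infusions.

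**Conclusion.** The concern holds as a gap in reporting and analysis, of modest weight. Section 9.4 leaves a secondary objective with point incidences only. The best possible result, 0 of 40, would leave serious-event rates up to 8.8% unexcluded (two-sided 95%), which includes the cited 6.1%. In the 20 patients treated during the randomised period the corresponding limit is 16.8%.

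These limits assume that all 40 patients receive FMT, that each patient counts once and that patients are independent. Fewer treated patients widen them (9.7% at 36). That the limits depend only on n and the count is a strength: the absence of an interval, an exposure denominator and a randomised comparison would matter whatever yardstick was chosen. The data would not be lost, but the safety conclusion they permit would not be fixed in advance.

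**What to change.** Amend section 9.4 as follows.

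1. For all patients with at least one FMT, counting from the first FMT, report the number and percentage with at least one serious event and with at least one FMT-related event, each with an exact (Clopper-Pearson) 95% interval. Show follow-up by group, because the early group is observed for up to 12 months from first FMT and the late group for up to 6.
2. From baseline to before the month 6 FMT, report all-cause adverse events and serious events by randomised group, counting from baseline in both, with a 95% interval for the difference by a named method. Do not compare FMT-related events with the untreated group, where that count is zero by design.
3. State that the safety conclusion is limited to the upper limit, so that 0 of 40 excludes only serious-event rates above about 8.8%.
4. Reconcile the safety set with the one-week rule in 9.7. Reconcile the adverse-event definition in 8.2.1 and the review wording in section 4 with the synopsis, so that control-period events are captured alike in both groups.

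The cost is a short paragraph in 9.4, some extra table columns and the wording changes in item 4. No patients, visits or procedures are added. The safety statement becomes somewhat less favourable, and the comparison in item 2 will be imprecise with 20 per group.

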Test product, dose and mode of administration, batch number to be provided by [name] lab at St. Joseph's Health Care, London, ON. For this study, fecal samples from healthy donors will be screened as per Health Canada guidelines. About 50-70g of the fecal sample is blended in 220ml saline in a Stomacher and filtered and transferred to an enema bag for transplantation. From here on this is known as "FMT" or "study medication".

Lot no. XXXXXX

Duration of treatment/study:

FMT rectal enema will be administered as scheduled per group, for up to 6 months.

Criteria for evaluation:

- Circulating cytokines levels (IL-1 β , IL-2, IL-4, IL-5, IL-6, IL-9, IL-10, IL-12p70, IL-13, IL-15, IL-17A, IL-17E/IL-25, IL-17F, IL-21, IL-22, IL-23, IL-27, IL-28A, IL-31, IL-33, GM-CSF, IFN γ , MIP-3 α , TNF α and TNF β).
- Gut microbiome through feces analysis
- Blood DNA bacteria
- Gut permeability through urine analysis
- All adverse events occurring during this study will be recorded. MS clinical functional status will be monitored using EDSS to assess any changes during the treatment period, as well as head MRI as a safety surrogate.

Statistical methods:

Adverse events will be coded using MedDRA dictionary. Incidence of adverse events by the severity, relationship to treatment, and outcome will be provided. Narratives of all serious adverse events and events causing death will be included. Laboratory parameters, vital signs and other safety parameters will be documented with the use of descriptive statistics.

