3.2 Secondary outcomes

We are also aiming to evaluate if FMT can possibly alter gut permeability through urinalysis and peripheral blood DNA bacteria. We also aim to evaluate treatment safety using the Expanded Disability Status Scale (EDSS) and MRI as surrogates for any paradoxical worsening in MS disease activity. We are monitoring adverse events to assess tolerability.

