8.0 ASSESSMENT OF SAFETY

8.1 Head MRI

A contrast head MRI will be performed at baseline, 6 months and 12 months for both groups as a safety measure to evaluate any subclinical activity or any paradoxical effect potentially caused by the FMT.

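### EDSS and MRI safety data are to be described without a contrast against the untreated group, and 20 per group cannot rule out paradoxical MS worsening

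*Combined protocol and SAP*

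**What the plan says.** The synopsis lists safety as a secondary objective and gives the purpose of MRI as "to rule out paradoxical effects; i.e. significant increase in MS activity". It defines such an increase as "5 or more newly enhancing white matter lesions in the brain compared to the previous scan". Section 3.2 uses EDSS and MRI "as surrogates for any paradoxical worsening in MS disease activity".

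Section 8.1 states "A contrast head MRI will be performed at baseline, 6 months and 12 months for both groups as a safety measure" but does not repeat the lesion threshold. No section gives a step size or confirmation rule for EDSS; the synopsis asks only that changes be monitored.

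Section 9.4 has two analysis statements that bear on this. For adverse events: "Incidence of adverse events by the severity, relationship to treatment, and outcome will be provided". For everything else: "Laboratory parameters, vital signs and other safety parameters will be documented with the use of descriptive statistics". Neither mentions randomised group, treatment period, a difference or an interval. The only between-group model in the plan, the mixed-design ANOVA, is in Section 9.3 under Biomarkers.

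Section 4 makes the late group an untreated control for the first six months. Tables 1 and 2 schedule EDSS at every visit and MRI at baseline, 6 and 12 months in both groups.

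**The concern.** Section 2 describes relapsing MS as a disease with its own episodes of worsening. A change from a patient's own baseline, or from the patient's own previous scan, therefore mixes any FMT effect with natural activity. Randomisation supplies a concurrent untreated group for months 0-6 that could help separate the two, but the analysis section does not say it will be used.

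Two things are at stake. A count of MRI or EDSS events without its control count can be read as harm or as reassurance, and nothing in the plan says which. And a report of few or no events, set beside an aim of ruling out paradoxical effects, could be taken to exclude a risk that the data leave open.

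**Working it through.** **Inputs.** 20 patients per group, 40 in total (synopsis; Section 4). All 40 are due to receive FMT: the early group from baseline to month 5, the late group from month 6 to month 11. The documents give no expected event rate and no margin for MRI or EDSS worsening, so there is no planned safety figure to reproduce. Section 9.1 calls the group size arbitrary. The type I error of 0.05 and power of 0.8 in Section 6.3 belong to the cytokine outcome.

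**Step 1: what zero events would show.** The exact (Clopper-Pearson) two-sided 95% upper limit solves (1 - p)^n = 0.025, so p = 1 - 0.025^(1/n).
- n = 20: 1 - 0.025^(1/20) = 16.8%
- n = 40 (both FMT periods pooled): 1 - 0.025^(1/40) = 8.8%

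With one-sided 95% limits, 1 - 0.05^(1/n), these become 13.9% and 7.2%. Section 9.6 plans no imputation, so missing scans widen them: 0 of 18 gives 18.5% and 0 of 36 gives 9.7% (two-sided).

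**Step 2: the month 0-6 contrast.** The Wilson upper limit for 0 of 20 is 1.96² / (20 + 1.96²) = 3.84 / 23.84 = 0.161. With 0 of 20 in both arms, the Newcombe 95% interval for the risk difference is 0 ± √(0.161² + 0²), or about -16 to +16 points. With 1 of 20 in both arms it is about -19 to +19. An exact unconditional interval (score-statistic ordering) is a little wider: about ±18 and ±20 points.

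**Step 3: how large a difference would stand out.** Smallest splits, out of 20 per arm, that reach two-sided Fisher p < 0.05:

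| Untreated events | FMT events needed | p | p with one fewer FMT event |
|---|---|---|---|
| 0 | 5 | 0.047 | 0.106 |
| 1 | 7 | 0.044 | 0.091 |
| 2 | 9 | 0.031 | 0.065 |

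**Step 4: power over a range of assumed rates.** These rates are assumptions, because the documents give none. The last column is a normal approximation.

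| Untreated v FMT rate | Fisher power, 20 per arm | Approx. n per arm for 80% power |
|---|---|---|
| 5% v 20% | 17% | 76 |
| 5% v 30% | 45% | 36 |
| 5% v 40% | 72% | 22 |
| 10% v 30% | 24% | 62 |

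**Step 5: who would be in the contrast.** Section 9.7 admits to all analyses patients who received one week of study treatment, and the synopsis defines study medication as FMT. Read literally, a late-group patient who worsens and leaves before the first FMT at month 6 is excluded. That removes control-period events from the very comparison that is needed.

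**The case against.** Descriptive safety reporting is normal in a trial that Section 9.1 calls exploratory proof of concept. That stands: the absence of a test is not the fault.

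Several stronger readings are tempting, and the documents do not support them.

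- *That MRI has no worsening rule.* It has a numerical per-patient rule in the synopsis. The gap is that the rule does not reach Sections 8.1 or 9.4 and has no analysis attached.
- *That the plan intends an uncontrolled or pooled summary, or means only.* Section 9.4 is silent. Descriptive statistics can be tabulated by group and can include patient counts. The defect is that this is left open.
- *That individual worsening would go unrecorded.* Section 8.2.1 counts worsening of a pre-existing condition during treatment, including disease progression, as an adverse event, and 9.4 promises narratives for serious ones. This captures some worsening patient by patient. It supplies no control comparison, because both listed conditions are tied to study treatment.
- *That the trial will report zero events as proof of safety.* The ruling-out wording appears once, in a synopsis bracket, and concerns MRI only. It may mean no more than checking each scan. Section 8.1 speaks of evaluating a paradoxical effect. The wording still promises more than the sample can give.
- *That the 6.1% serious adverse event rate for lower routes in Section 2.7 shows what would be missed.* That rate covers serious events of all kinds in other populations and says nothing about MS worsening.
- *That comparing the arms would settle the question.* Steps 2 to 4 show that it would not. The EDSS contrast is also open label, and no blinded rater is described.

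**Conclusion.** The point holds in a limited form. EDSS and MRI are the plan's instruments for its MS-specific safety question, yet the analysis section names no summary by randomised group or period, does not carry the MRI rule forward, and has no EDSS worsening definition. The concurrent control that the design already provides is therefore not put to use.

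Separately, ruling out paradoxical worsening is not attainable at this size. Zero events in 20 treated patients is compatible with a true rate up to 16.8%, zero in 40 with up to 8.8%, and zero in both arms with a difference of about 16 points either way (about 18 by the exact method). These figures assume complete follow-up and one yes/no outcome per patient in each period. The power figures also rest on assumed event rates.

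This is a worthwhile, inexpensive correction to analysis and wording. It does not make the design invalid.

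**What to change.** In Section 9.4, for months 0-6 and by randomised group, report the number of patients meeting the existing MRI rule and the number meeting an EDSS worsening definition fixed before analysis. Give each as a risk difference with an exact 95% CI, labelled as estimation and not as a powered test. Repeat the MRI rule in Sections 8.1 and 9.4.

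State that this comparison includes late-group patients who leave before their first FMT, notwithstanding Section 9.7. State also how a late-group month-6 scan is handled if it follows the first FMT: Section 6.2.2 places EDSS before FMT at each visit but does not say so for MRI.

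In the synopsis, change the purpose of MRI from ruling out to screening for paradoxical effects, and give the upper limits that zero events would leave (16.8% for 20, 8.8% for 40).

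The cost is text in Section 9.4, Section 8.1 and the synopsis, plus agreement on one EDSS definition. No visit or measurement is added. The drawbacks are that the stated safety claim becomes weaker, the intervals will be wide enough to look uninformative, and the EDSS contrast remains exposed to open-label assessment and should be reported with that caveat.
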